### **6.3        Serious Adverse Events**

#### **6.3.1      Definitions**

A serious adverse event is an undesirable sign, symptom or medical condition which:

- is fatal or life-threatening
- results in persistent or significant disability/incapacity
- constitutes a congenital anomaly/birth defect
- requires inpatient hospitalization or prolongation of existing hospitalization, unless hospitalization is for:
- routine treatment or monitoring of the studied indication, not associated with any deterioration in condition (specify what this includes)
- elective or pre-planned treatment for a pre-existing condition that is unrelated to the indication under study and has not worsened since the start of study drug
- treatment on an emergency outpatient basis for an event not fulfilling any of the definitions of a SAE given above and not resulting in hospital admission
- social reasons and respite care in the absence of any deterioration in the patient's general condition
- is medically significant, i.e., defined as an event that jeopardizes the patient or may require medical or surgical intervention to prevent one of the outcomes listed above

#### **6.3.2      Reporting**

The principal investigator has the obligation to report all serious adverse events to the FDA, IRB, and Novartis Pharmaceuticals Drug Safety and Epidemiology Department (DS&E).

All events reported to the FDA by the investigator are to be filed utilizing the Form FDA 3500A (MedWatch Form).

To ensure patient safety, every SAE, regardless of suspected causality, occurring

- after the patient has provided informed consent and until at least 30 days after the patient has stopped study treatment/participation
- after protocol-specified procedures begin and 30 days after the patient has stopped study treatment
- after the start of any period in which the study protocol interferes with the standard medical treatment given to a patient (e.g., treatment withdrawal during washout period, change in treatment to a fixed dose of concomitant medication) and until 30 days after the patient has stopped study treatment

must be reported to Novartis within 24 hours of learning of its occurrence (**[contact]**). This includes serious, related, labeled (expected) and serious, related, unlabeled (unexpected) adverse experiences. All deaths during treatment or within 30 days following completion of active protocol therapy must be reported within 5 working days.

Any SAEs experienced after this 30 days period should only be reported to Novartis if the investigator suspects a causal relationship to the study drug. Recurrent episodes, complications, or progression of the initial SAE must be reported as follow-up to the original episode within 24 hours of the investigator receiving the follow-up information. A SAE occurring at a different time interval or otherwise considered completely unrelated to a previously reported one should be reported separately as a new event. The end date of the first event must be provided.

The original copy of the SAE Report and the fax confirmation sheet must be kept within the Trial Master File at the study site.

CONFIDENTIAL

This document and information is the property of the NYU School of Medicine and Langone Medical Center. Do not disclose or use except as authorized in writing by the study IND sponsor

Follow-up information is sent to the same fax number as the original SAE Report Form was sent, using a new fax cover sheet, stating that this is a follow-up to the previously reported SAE, and giving the date of the original report. Each re-occurrence, complication, or progression of the original event should be reported as a follow-up to that event regardless of when it occurs. The follow-up information should describe whether the event has resolved or continues, if and how it was treated, and whether the patient continued or withdrew from study participation.

If the SAE is not previously documented in the Everolimus Investigator Brochure or Package Insert (new occurrence) and is thought to be related to the Novartis study drug, a DS&E associate may urgently require further information from the investigator for Health Authority reporting. Novartis may need to issue an Investigator Notification (IN), to inform all investigators involved in any study with the same drug that this SAE has been reported. Suspected Unexpected Serious Adverse Reactions (SUSARs) will be collected and reported to the competent authorities and relevant ethics committees in accordance with Directive 2001/20/EC or as per national regulatory requirements in participating countries.

### **6.3.3 Investigator reporting: notifying the NYULMC IRB**

This section describes the requirements for safety reporting by investigators who are NYULMC faculty, affiliated with a NYULMC research site, or otherwise responsible for safety reporting to the NYULMC IRB. The NYU Langone Medical Center IRB (NYULMC IRB) requires expedited reporting of those events related to study participation that are unforeseen and indicate that participants or others are at increased risk of harm. The NYULMC IRB will not acknowledge safety reports or bulk adverse event submissions that do not meet the criteria outlined below. The NYULMC IRB requires researchers to submit reports of the following problems within 5 working days from the time the investigator becomes aware of the event:

A reportable event is an event that occurs at any time during or after the research study, which in the opinion of the principal investigator is:

- **Unexpected:** An event is “unexpected” when its specificity and severity are not accurately reflected in the protocol-related documents, such as the IRB-approved research protocol, any applicable investigator brochure, and the current IRB-approved informed consent document and other relevant sources of information, such as product labeling and package inserts.

**AND**

- **Related to the research procedures:** An event is “related to the research procedures” if in the opinion of the principal investigator or sponsor, the event was more likely than not to be caused by the research procedures.

**AND**

- **Harmful:** Harmful includes causing harm to participants or others, or placing them at increased risk of harm.

### **Reporting Process**

Unanticipated problems posing risks to subjects or others as noted above will be reported to the NYULMC IRB or St Barnabas Medical Center IRB using the form: “Reportable Event Form” or as a written report of the event (including a description of the event with information regarding its fulfillment of the above criteria, follow-up/resolution and need for revision to consent form and/or other study documentation).

Copies of each report and documentation of IRB notification and receipt will be kept in the Clinical Investigator’s study file.

### **Other Reportable events:**

For clinical drug trials, the following events are also reportable to the NYULMCIRB:

CONFIDENTIAL

This document and information is the property of the NYU School of Medicine and Langone Medical Center. Do not disclose or use except as authorized in writing by the study IND sponsor

- Any adverse experience that, even without detailed analysis, represents a serious unexpected adverse event that is rare in the absence of drug exposure (such as agranulocytosis, hepatic necrosis, Stevens-Johnson syndrome).
- Any adverse event that would cause the sponsor to modify the investigators brochure, protocol or informed consent form, or would prompt other action by the IRB to assure protection of human subjects.
- Information that indicates a change to the risks or potential benefits of the research, in terms of severity or frequency. For example:
  - An interim analysis indicates that participants have a lower rate of response to treatment than initially expected.
  - Safety monitoring indicates that a particular side effect is more severe, or more frequent than initially expected.
  - A paper is published from another study that shows that an arm of your research study is of no therapeutic value.
- Change in FDA safety labeling or withdrawal from marketing of a drug, device, or biologic used in a research protocol.
- Breach of confidentiality
- Change to the protocol taken without prior IRB review to eliminate apparent immediate hazard to a research participant.
- Incarceration of a participant when the research was not previously approved under Subpart C and the investigator believes it is in the best interest of the subject to remain on the study.
- Complaint of a participant when the complaint indicates unexpected risks, or the complaint cannot be resolved by the research team.
- Protocol violation (meaning an accidental or unintentional deviation from the IRB approved protocol) that in the opinion of the investigator placed one or more participants at increased risk, or affects the rights or welfare of subjects.

#### **6.3.4 Investigator reporting: Notifying a non-NYULMC/ IRB**

Not Applicable

#### **6.3.5 Sponsor reporting: Notifying the FDA**

The study IND sponsor is required to report certain study events in an expedited fashion to the FDA. These written notifications of adverse events are referred to as IND safety reports. The following describes the safety reporting requirements by timeline for reporting and associated type of event:

- ***Within 7 calendar days (via telephone or facsimile report)***  
Any study event that is:
  - associated with the use of the study drug,
  - unexpected,
  - fatal or life-threatening
- ***Within 15 calendar days (via written report)***  
Any study event that is:
  - associated with the use of the study drug,
  - unexpected, and
  - serious, but not fatal or life-threatening

-or-

  - a previous adverse event that was not initially deemed reportable but is later found to fit the criteria for reporting (reporting within 15 calendar days from when event was deemed reportable).

Any finding from tests in laboratory animals that:

CONFIDENTIAL

This document and information is the property of the NYU School of Medicine and Langone Medical Center. Do not disclose or use except as authorized in writing by the study IND sponsor

- suggest a significant risk for human subjects including reports of mutagenicity, teratogenicity, or carcinogenicity.

### **Additional reporting requirements**

Sponsors are also required to identify in IND safety reports all previous reports concerning similar adverse events and to analyze the significance of the current event in light of the previous reports.

### **Reporting Process**

Adverse events may be submitted on FDA Form 3500A or in a narrative format. If supplied as in a narrative format, the minimum information to be supplied is noted above at the beginning of section 8.3. The contact information for submitting IND safety reports is noted below:

#### **6.3.6 Sponsor reporting: Notifying participating investigators**

Not Applicable

#### **6.4 Unblinding Procedures**

*Not applicable.*

#### **6.5 Stopping Rules**

A Data Safety Monitoring Program (DSMP) will be established to monitor adverse events and study safety. Prior to commencement of the study, the rate of infection and impaired wound healing associated with routine two-stage epilepsy surgeries as will be performed in this study over the past 5 years will be determined for each epilepsy surgeon ([name] and [name]). A statistician from the NYU School of Medicine Biostatistics Department will provide blinded reports to the Data Safety Monitoring Committee (DSMC). The PI, [name], [name], [name] and [name] (co-investigators) will aid in reviewing all patients during the treatment period and throughout the post-treatment monitoring period. They will review all cases and if it is deemed that the serious adverse event(s) are related to study drug, the study will be terminated for that subject. If two patients among the 9 treated with everolimus develop a) impaired surgical wound healing or if three patients among the 9 develop b) serious infection, including wound site infection. Any case of wound site infection complicated by a wound healing problem will NOT be considered a wound healing problem.

#### **Medical Monitoring**

It is the responsibility of the Principal Investigator to oversee research subject safety. This safety monitoring will include careful assessment and appropriate reporting of adverse events as noted above, as well as the construction and implementation of a site data and safety-monitoring plan (see section 10. Auditing, Monitoring and Inspecting). Medical monitoring will include a regular assessment of the number and type of serious adverse events..

It is the responsibility of the IND Sponsor to assess research subject safety.

Data Safety Monitoring Program (DSMP), Data Safety Monitoring Committee (DSMP): The investigators will review all safety data after each three subject treatment cohort has completed the trial. All safety data will be sent to the DSMB after every 3 patients have completed the protocol or if there is any serious adverse event that may possibly be related to the study.

For this pilot, open-label exploratory clinical trial, given the potential risk that may be associated with a 7-21 day trial of everolimus treatment prior to elective epilepsy surgery in TSC and FCD patients, a DSMP will be established. Monitoring will be performed on a regular basis throughout the participant accrual, treatment, and follow-up. Dose Limiting Toxicity is not anticipated to be an issue since the doses used are standard in prior research studies and now FDA approved for patients with TSC. However, all adverse events will be recorded and reviewed.

CONFIDENTIAL

This document and information is the property of the NYU School of Medicine and Langone Medical Center. Do not disclose or use except as authorized in writing by the study IND sponsor

Any adverse event occurring during, or after 30 days of last treatment will be documented by the epilepsy neurologist member of the DSMP, including fatigue, rash, anorexia, mucositis, edema, cough, thromboembolism, nausea, vomiting, stomatitis, sinusitis, bronchitis, pneumonia, abscess, leukopenia, or hyperlipidemia.

Because of the specific concern regarding potential wound healing problems and wound infection resulting from treatment with everolimus prior to elective epilepsy surgery, wound status will be carefully monitored, specifically by a neurosurgeon.

The site of the planned surgical incision will be inspected by both of the DSMP members 5 days after initiating therapy (prior to surgery), and then at weekly intervals, beginning one week after surgery until six weeks after surgery. The neurosurgeon will document wound status with digital photography.

Blood test surveillance for possible infection will be performed at the same time intervals (7-10 days before starting everolimus, 7-21 days after starting everolimus, and 3-10 days after discharge from the hospital, and then 3 and 6 weeks after surgery if any evidence of infection is identified on examination or the post-hospital discharge blood test) consisting of a complete blood count (CBC) with differential and C-reactive protein (CRP).

Any abnormality will be documented for review by the DSMP. Since no ideal objective scoring system exists for assessing surgical site adverse events [39,40], any wound breakdown, dehiscence or infection will be considered a serious adverse event, and will be reported to the participating site IRB and to the NINDS, and the decision will be made as to whether the study should be terminated.

Individual subject participation in the study will be terminated if the DSMC finds any of the following unexpected new findings in a subject:

- 1) Documented wound infection requiring surgery
- 2) Documented wound dehiscence requiring surgery
- 3) Persistent fever above 101 degrees F and abnormally elevated serum wbc count and ESR and CRP in the absence of a known cause
- 4) Documented bacterial meningitis

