#### **4.4 Early Withdrawal of Subjects**

##### **4.4.1 When and How to Withdraw Subjects**

A subject may withdraw from the study due to:

- 1) Improvement in seizure activity to an extent that the patient and/or parents/legal guardians elect to forego epilepsy surgery for treatment with everolimus,
- 2) Difficult complying with protocol requirements or
- 3) A decision to withdrawal for personal reasons or adverse effects that are less severe than those that lead to mandatory discontinuation of the treatment phase.

A subject will be withdrawn from the study if any of the following are present:

- 1) The subject develops a systemic bacterial or fungal infection.
- 2) The subject develops a CTAE grade 3 or 4 (severe) event.
- 3) The patient and study will be terminated if he or she is the second case of impaired surgical wound healing or the third case of serious infection, including infection of the wound site, among the 18 everolimus-treated patients.

Given the short duration of treatment, there are no known or postulated safety concerns related to abrupt discontinuation after this duration and dosage of therapy with everolimus. Any subject who elects to withdraw from the study will be recommended to discontinue the everolimus therapy, but if they desire a tapering schedule, one will be provided with exception for those patients going forward with surgery, when everolimus will be completely discontinued prior to surgery.

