##### **4.4.2 Data Collection and Follow-up for Withdrawn Subjects**

For any subject who withdraws from the study, we will obtain serum levels of everolimus on the last date they take the medication (or as close). We will also collect all safety data and seizure activity calendars. Since these patients will be entered into the study only 7 to 21 days before brain surgery, they typically have close contact with the neurosurgeon, epileptologist, and clinical staff of the epilepsy center. We will actively pursue with phone calls to patient, parents, and legal guardians to determine the cause for withdrawal and obtain as complete data as possible regarding study data elements during the baseline and treatment phase. We will utilize up to 5 phone calls and 2 certified letters to any patients who withdraw but for whom we do not have complete study records.

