#### Study drug dosing: (ACTIVE PATIENTS ONLY)

- On the day of surgery, the patient will take their last dose of everolimus with a 30 cc or less of water shortly after awakening and at least 3 hours before surgery
- A detailed seizure history during the prior week. A blood sample will be used for investigation per the IRB-approved protocol. This will include everolimus serum levels, systemic cytokines and mTOR activity levels. These samples will be batched and stored in -80 freezer until requested for analysis. )

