### **6.2 Adverse events**

#### **6.2.1 Definitions and reporting**

Adverse events that begin or worsen after informed consent should be recorded in the Adverse Events CRF. Conditions that were already present at the time of informed consent should be recorded in the Medical History page of the patient's CRF. Adverse event monitoring should be continued for at least 30 days (or 5 half-lives, whichever is longer) following the last dose of study treatment. Adverse events (including lab abnormalities that constitute AEs) should be described using a diagnosis whenever possible, rather than individual underlying signs and symptoms. When a clear diagnosis cannot be identified, each sign or symptom should be reported as a separate AdverseEvent.

The occurrence of adverse events should be sought by non-directive questioning of the patient at each visit during the study. Adverse events also may be detected when they are volunteered by the patient during or between visits or through physical examination, laboratory test, or other assessments. As far as possible, each adverse event should be evaluated to determine:

1. The severity grade (CTAE Grade 1-4)
2. Its duration (Start and end dates or if continuing at the Safety Follow-up Visit)
3. Its relationship to the study treatment (Reasonable possibility that AE is related: No, Yes)
4. Action taken with respect to study or investigational treatment (none, dose adjusted, temporarily interrupted, permanently discontinued, hospitalized, unknown, not applicable)
5. Whether medication or therapy was given (no concomitant medication/non-drug therapy, concomitant medication/non-drug therapy)
6. Outcome (not recovered/not resolved, recovered/resolved, recovering/resolving, recovered/resolved with sequelae, fatal, unknown)
7. Whether it is serious, where a serious adverse event (SAE) is defined as in Section 8.2.1

All adverse events should be treated appropriately. Such treatment may include changes in study drug treatment including possible interruption or discontinuation, starting or stopping concomitant treatments, changes in the frequency or nature of assessments, hospitalization, or any other medically required intervention. Once an adverse event is detected, it should be followed until its resolution, and assessment should be made at each visit (or more frequently, if necessary) of any changes in severity, the suspected relationship to the study drug, the interventions required to treat it, and the outcome.

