#### **Data Safety Monitor Details:**

*The enrolled subjects will be monitored:*

Drug

- Patients will be routinely monitored for adverse events via clinical evaluations and phone visits
- Subjects will have the research coordinator's phone number to call in case of need to report side effects on days not scheduled for clinical evaluation or phone visit.

PHI

- All PHI will be kept in locked filing cabinet at NYU Comprehensive Epilepsy Center and/or entered into REDCap (NYU secure data management system) with access given only to study personnel

*Dropouts will be monitored:*

- Dropouts will have a final visit to complete their enrollment and receive instructions for tapering off of Everolimus.

.

*Primary and secondary efficacy endpoints will be monitored:*

The primary study endpoints of the safety and tolerability of everolimus in children and young adults and the establishment of optimal dose will be monitored via:

- Side Effects in children and subjects where caregiver reports and in adults that are able to self report.
- Evaluation of seizure diary at clinical evaluations and phone visits

The secondary study endpoint of change in frequency from baseline will be monitored via:

- Evaluation of seizure diary at clinical evaluations and phone visits

*Reportable events will be monitored using an accepted scale:*

No, there will be no accepted scale for monitoring reportable events. All reportable events will be followed until resolution, stabilization, or until it has been determined that the study treatment or participation is not the cause. If the reportable event is still ongoing at the end of the study, it will be followed until final outcome has been reached.

*Describe the frequency of monitoring:*

The Independent monitor will evaluate every 12 months after the first patient receives the initial dosage of everolimus

*Interim analysis will take place:*

No, interim analysis will not take place unless requested by the IRB.

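### The withdrawal and termination rules end study participation rather than only study drug when a key safety event occurs, and nothing keeps those patients on the post-operative wound surveillance.

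*Combined protocol and SAP*

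**What the plan says.** **Rules that end participation**

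- Section 6.5, Medical Monitoring: "Individual subject participation in the study will be terminated if the DSMC finds any of the following unexpected new findings in a subject". The list covers wound infection or dehiscence needing surgery, unexplained persistent fever with raised markers, and bacterial meningitis.
- Section 4.4.1: "A subject will be withdrawn from the study if any of the following are present". The list includes "The subject develops a systemic bacterial or fungal infection" and "The subject develops a CTAE grade 3 or 4 (severe) event".
- Sections 6.5 and 7.1 (Data Safety Monitoring Plan) end the study for a subject whose serious adverse event is judged drug-related. Section 6.5 classes every wound breakdown, dehiscence or infection as serious, so this rule can also reach wound events that need no operation.
- Section 5.9: "On the day of surgery, the patient will take their last dose of everolimus".

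**Rules that continue observation**

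- Section 4.4.2 collects all safety data on patients who withdraw. It then describes calls and letters to "obtain as complete data as possible regarding study data elements during the baseline and treatment phase".
- Section 6.2.1 monitors adverse events for at least 30 days after the last dose (or 5 half-lives if longer) and adds: "Once an adverse event is detected, it should be followed until its resolution".
- Section 6.3.2 requires serious adverse event reporting for 30 days after treatment or participation stops, and follow-up reports of complications.
- Section 7.1 follows ongoing reportable events to final outcome, but also says: "Dropouts will have a final visit to complete their enrollment and receive instructions for tapering off of Everolimus".
- Section 7.3 (Subject Population(s) for Analysis) keeps everyone who took a dose in the safety analysis.

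**Planned surveillance**

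Section 6.5 plans weekly wound inspection from one to six weeks after surgery, with blood tests at 3 and 6 weeks if infection is suspected. Visits 4 to 6 (sections 5.10 to 5.13) add wound checks in hospital and 3 to 10 days after discharge.

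**The concern.** Safety is declared the primary analysis, and wound healing and infection are its focus. The events that end participation are those same events, or earlier toxicities in patients who may still be operated on. Because the last dose precedes the operation, there is usually no everolimus left to stop when a post-operative wound event occurs. Ending participation then mainly affects what is observed next.

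Safety data could be incomplete in two ways. A patient withdrawn before surgery for a toxicity that resolves has no stated route to wound inspection if surgery goes ahead. A patient terminated after one post-operative event has no stated place on the remaining inspections, where a second event might be found. Both stay in the safety denominator. Two sites or two coordinators could follow the same text and collect different data.

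**Working it through.** The plan states no figure on this point, so the check is mainly a comparison of passages, with arithmetic for scale.

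**1. Which monitoring window governs.** Section 1.5 gives a half-life of 30 hours. 5 × 30 h = 150 h = 6.25 days, which is shorter than 30 days. The 30-day minimum therefore applies.

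**2. What that window covers.** Weekly inspections from week 1 to week 6 fall on post-operative days 7, 14, 21, 28, 35 and 42. Assume surgery takes place on day D of a D-day course, as planned, and the last dose is on day s. The window then ends on post-operative day 30 − (D − s).

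| Planned course D | Last dose s | Window ends, post-op day | Inspection dates inside (of 6) |
|---|---|---|---|
| any | day of surgery | 30 | 4 |
| 7 | 3 | 26 | 3 |
| 7 | 1 | 24 | 3 |
| 14 | 1 | 17 | 2 |
| 21 | 3 | 12 | 1 |
| 21 | 1 | 10 | 1 |

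A patient stopping one or two days before surgery still has 4 dates inside (30 − 2 = 28). The range for early withdrawal is therefore 1 to 4. The 6-week blood test (day 42) is always outside. The 3-week test (day 21) is inside only if dosing stopped no more than 9 days before surgery (30 − 9 = 21).

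These are dates spanned by general adverse event monitoring. Section 6.2.1 relies largely on questioning at visits; it does not say that anyone inspects the wound on those dates.

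**3. How often the wording could come into play.** Section 7.3 gives background rates of under 2% for wound healing problems and a mean of 5.3% for infection. Taking 2% and assuming independence, the chance of either in one patient is 1 − 0.98 × 0.947 = 7.2%. Among 9 patients the expected number is 9 × 0.072 = 0.65, and P(at least one) = 1 − 0.928⁹ = 48.9%. This is an upper bound for the section 6.5 wound criteria, which require surgery. It leaves out any drug effect and all other Grade 3 or 4 events.

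**4. The study stopping rule.** P(X ≥ 2) = 1 − (1 − p)ⁿ − n·p·(1 − p)ⁿ⁻¹, with n the number of treated patients fully observed.

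| Wound-problem rate p | n = 9 | n = 8 | n = 7 |
|---|---|---|---|
| 2% (plan's background ceiling) | 1.3% | 1.0% | 0.8% |
| 12.3% (heart transplant, section 1.4) | 31% | 26% | 21% |
| 19% (kidney transplant, section 1.4) | 53% | 47% | 40% |

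The columns for 8 and 7 assume that one or two patients contribute no wound observation at all, which is the extreme case. The transplant rates are illustrations only. For infection, P(3 or more of 9) is 1.0% at 5.3%, and 0.03% to 3.6% over 1.6% to 8.6%.

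**5. Classification.** A wound problem secondary to wound site infection counts as an infection, so later observation can move a case from one stopping count to the other.

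**The case against.** A reader might infer that follow-up is cut, that wound and infection rates are biased low, and that the stopping counts lose cases. The documents do not support that reading.

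- The event that triggers termination has already been recorded. The stopping rules in sections 6.5 and 7.1 count among the 9 treated, not among completers, and every dosed patient is in the safety set.
- Section 4.4.2 collects all safety data without a time limit. The phrase naming the baseline and treatment phase belongs to a later sentence on retrieval effort; it omits the post-operative period but does not exclude it.
- Section 6.3.2 applies after participation ends. Read from that point, a patient terminated on post-operative day 12 or later is covered to day 42 (12 + 30). This is a reporting duty, however, and adds little for someone withdrawn before surgery.
- The remark in section 4.4.1 about going forward with surgery concerns patients who choose to withdraw. No passage says that patients withdrawn for infection or severe toxicity are operated on as planned, or that their wound risk is higher.
- The single final visit in section 7.1 is for dropouts, a term not clearly extended to patients terminated for safety.
- Termination can also affect research tissue collection at a second operation (section 5.11), so ending follow-up is not its only possible effect.
- Section 1.5 describes transplant patients as chronically ill and otherwise immunosuppressed, and this trial excludes several of those risks.

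All of this stands. It limits the point to a conflict of wording and a gap in scheduled surveillance. It does not close the gap: collecting safety data and following a detected event do not say who inspects the wound, or when, after a patient is off study.

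**Conclusion.** The point holds in limited form. Sections 4.4.1, 6.5 and 7.1 end participation, not only dosing, on events central to the primary safety analysis. This conflicts with the continuing-observation provisions in sections 4.4.2, 6.2.1, 6.3.2 and 7.1. No passage keeps a withdrawn or terminated patient on Visits 4 to 6, the weekly inspections or the conditional blood tests.

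If only the 30-day window from last dose survives, 2 of 6 inspection dates fall outside it for a patient dosed to surgery, and 2 to 5 for one withdrawn earlier, assuming surgery on the planned date. A later wound or infection event could then be missed. With 9 treated and triggers of 2 and 3, one unobserved case can decide whether the study stops. At the plan's own 2% ceiling the wound rule would fire about 1% of the time with or without those patients. The larger differences appear only at transplant rates and with complete loss of observation.

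This is a text reconciliation that would improve ascertainment of the primary safety outcome. It should be made, but it does not undermine the safety analysis as a whole.

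**What to change.** 1. In sections 4.4.1, 6.5 and 7.1, define two separate states: study drug discontinued, and withdrawn from the study.
2. State that a dosed patient who meets a safety criterion and has the operation continues the scheduled post-operative safety assessments (Visits 4 to 6 and the section 6.5 wound and blood surveillance) unless consent to data collection is withdrawn.
3. In section 4.4.2, extend active data retrieval to the post-operative period, and say that it covers patients withdrawn or terminated by the study as well as those who choose to leave.
4. Reconcile related passages. Section 4.4.1 withdraws patients for Grade 3 or 4 events, and section 5.3 turns interruption for toxicity into discontinuation, while Tables 3 and 4 allow interruption and restart for many such events. The taper instruction for dropouts in section 7.1 differs from section 4.4.1, where a taper is optional and not for those going to surgery. Section 4.4.1 also counts stopping events among 18 treated patients, against 9 elsewhere. Which clinical rule should apply is for the sponsor and investigators to decide.

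The cost is protocol wording and a few extra post-operative visits for discontinued patients.
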